7.1.2 Procedures for Handling Patients who are Incorrectly Initiated on Study Treatment

Patients who do not meet the inclusion/exclusion criteria should not, under any circumstances, receive study treatment. There can be no exceptions to this rule.

Where patients that do not meet the inclusion/exclusion criteria are incorrectly started on treatment, or where patients subsequently fail to meet the study criteria post initiation, the Investigator should inform the AstraZeneca Medical Monitor immediately.

Any patient who is found to have failed to meet the selection criteria, but has started treatment, will be removed from the study following completion of safety follow-up activities. Every effort should be made to ensure ineligible patients complete all safety follow-up activities. The Medical Monitor is to ensure all such contacts are appropriately documented.

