7 DISCONTINUATION OF STUDY TREATMENT AND PATIENT DISCONTINUATION/WITHDRAWAL - CORE

7.1 Discontinuation of Study Treatment

Patients who permanently discontinue study treatment will continue to have follow-up assessments per the SoA. Patients will be permanently discontinued from study treatment if the following criteria are met:

- Patient decision. The patient is at any time free to discontinue study treatment, without prejudice to further treatment. A patient who discontinues study treatment is normally expected to continue to participate in the study (eg, for safety and survival follow-up) unless they specifically withdraw their consent to all further participation in any study procedures and assessments.
- Investigator decision
- Occurrence of any AE that, in the opinion of the Investigator or AstraZeneca contraindicates further dosing
- Pregnancy or intent to become pregnant
- Patients incorrectly initiated on study treatment (Section 7.1.2)
- Severe noncompliance with the study protocol that, in the opinion of the Investigator or AstraZeneca, warrants withdrawal from study treatment (eg, refusal to adhere to scheduled visits)
- The discovery of an unexpected, significant, or unacceptable risk to the patients enrolled in the study
- Decision to modify the development plan of the drug
- Initiation of alternative anticancer therapy including another investigational agent
- Confirmed disease progression ([Appendix J](#) and [Appendix K](#))
- Death

All patients who are discontinued from study treatment should complete protocol-specified procedures for discontinuation of study treatment and follow-up procedures. Discontinued patients will be followed for survival, either through direct contacts or by collecting public records (eg, death certificates) as allowed by local laws.

The end of treatment (EoT) visit should be performed as soon as the patient is permanently discontinued from study treatment. The reason for discontinuation should be documented in the source document and the appropriate section of the eCRF.

Patients may withdraw from any aspects of the optional exploratory research at any time,

without prejudice to further treatment and independent of any decision concerning participation in other aspects of the main study. Procedures for withdrawal from the exploratory research are outlined in Appendix [C 2](#).

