7.1.1 Procedures for Discontinuation of Study Treatment

Discontinuation of study treatment does not affect the patient's participation in the study. A patient who decides to discontinue the study treatment will always be asked about the reason(s) for discontinuation and the presence of any AE. The patient should continue attending subsequent study visits, and data collection should continue according to the study protocol. If the patient does not agree to continue to attend study visits in person, where possible, a modified follow-up must be arranged to ensure the collection of endpoints and safety information. The approach taken should be recorded in the medical records. A patient that agrees to modified follow-up is not considered to have withdrawn consent or to have withdrawn from the study.

Patients who are permanently discontinued from further receipt of study treatment, regardless of the reason, will be identified as having permanently discontinued treatment, followed by entry into follow-up. Patients who have permanently discontinued from further receipt of study treatment will need to be recorded in the IRT.

All patients will be followed for survival until the end of the study. Survival information may be obtained via telephone contact with the patient, patient's family, or by contact with the patient's current physician. Patients who decline to return to the site for evaluations should be contacted by telephone, following the timing and procedures indicated in the SoA, as an alternative.

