
 To estimate the preliminary antitumor activity of AZD0466 by assessment of DoR in patients with advanced haematological malignancies. 	
 DoR will be defined as the time from the date of first documented response (CR+CR_i) until date of documented progression, relapse or failure per Appendix J and Appendix K or death due to any cause. The analysis will include all dosed patients as intended who have a confirmed response (CR or CR_i), regardless of whether the patient withdraws from study treatment or receives another anticancer therapy. The measure of interest are the percentiles of DoR.

Table 13 Secondary Objectives - Module 1

Objectives	Estimand description
Overall Survival (OS)	

 To estimate the preliminary antitumor activity of AZD0466 by assessment of OS in patients with advanced haematological malignancies. 	
 OS is defined as time from date of first dose until the date of death due to any cause. The comparison will include all dosed patients as intended, regardless of whether the patient withdraws from therapy or receives another anticancer therapy. The measures of interest are the median OS and landmarks at 6 and 12 months of OS.

ALL, acute lymphocytic leukaemia; AML, acute myeloblastic leukaemia; CR, complete remission; CR_i, incomplete haematological response; DoR, duration of response; OS, overall survival; TTR, time to response

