11.3.1 Inclusion Criteria

Refer to Section 5.1 of the core protocol for the common inclusion criteria applicable to Module 1 Part A dose escalation and Module 1 Part B dose expansion. Additional inclusion criteria for each cohort of Module 1 Part B dose expansion are listed below. Eligible patients with relapsed or refractory AML or ALL will be enrolled to the cohorts according to the inclusion criteria described below.

Expansion Cohort B1

1. Patients must have a diagnosis of AML with a prior history of MPN which is histologically proven based on criteria established by the WHO as documented by medical records.
2. Patients must have received ≤ 2 prior lines of treatment for AML; prior treatment with venetoclax is permitted. A line of treatment is defined as a recognised regimen, as per local or national guidelines, of which the patient has received at least one dose, following which they have relapsed or had refractory disease as defined in Appendix J.

Expansion Cohort B2

1. Patients must have a histologically proven diagnosis of AML, which is based on criteria established by WHO as documented by medical records with a *TP53* mutation. *TP53* status already determined in accordance with local/institutional practice can be used for enrolment but needs to be confirmed centrally. Patients with AML who have had a prior history of MPN are ineligible.

2. Patients must have received ≤ 3 prior lines of treatment for AML; prior treatment with venetoclax is permitted. A line of treatment is defined as a recognised regimen, as per local or national guidelines, of which the patient has received at least one dose, following which they have relapsed or had refractory disease as defined in [Appendix J](#).

Expansion Cohort B3

1. Patients must have a diagnosis of AML, which is histologically proven based on criteria established by WHO as documented by medical records. Patients with AML with the *TP53* mutation (as described for Cohort B2) or AML who have had a prior history of MPN (as described in Cohort B1) are ineligible.
2. Patients must have been previously treated with venetoclax (either as monotherapy or in combination) and have received ≤ 3 prior lines of treatment. A line of treatment is defined as a recognised regimen, as per local or national guidelines, of which the patient has received at least one dose, following which they have relapsed or had refractory disease as in [Appendix J](#).

Expansion Cohort B4

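### Protocol 7.1.2 ends study participation for dosed patients later found ineligible, although 7.1, 7.1.1, Section 8 and the all-dosed survival analysis need their follow-up to continue

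*Protocol*

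**What the plan says.** **Removal.** Protocol 7.1.2 covers patients who started treatment without meeting the criteria and patients who fail to meet them after starting. Such a patient "will be removed from the study following completion of safety follow-up activities". Section 8 (Follow-up Period) and 8.3.1 set safety follow-up at 28 days after the last dose.

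**Continued follow-up.** Protocol 7.1 lists incorrect initiation, with a cross-reference to 7.1.2, among the reasons for stopping study treatment. For everyone who stops, it says "Patients who permanently discontinue study treatment will continue to have follow-up assessments per the SoA". Section 7.1.1 adds "Discontinuation of study treatment does not affect the patient's participation in the study" and "All patients will be followed for survival until the end of the study". Section 8 requires disease follow-up until progression or withdrawal of consent, monthly survival contact until withdrawal of consent or end of study, and relapse follow-up of CR and CRi patients until death.

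**Analysis.** Protocol Table 21 and SAP Table 5 define the intention-to-treat set as all patients with at least one dose, with no eligibility condition. For overall survival, protocol Table 13 states: "The comparison will include all dosed patients as intended, regardless of whether the patient withdraws from therapy". SAP 7.2.1.1 ends survival contacts for death, loss to follow-up, study closure or withdrawal of consent. Ineligibility is not on that list. SAP 4.6.2.1 reports dosed patients who breached the entry criteria as important deviations and does not exclude them.

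**Cohort B2.** Protocol 11.3.1 says a local TP53 result "can be used for enrolment but needs to be confirmed centrally". It does not say what happens to a patient whose result is not confirmed.

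**The concern.** A site cannot both remove a patient 28 days after the last dose and contact that patient monthly until the study ends. If it follows 7.1.2, the patient stays in the denominator of the all-dosed analyses while active collection of the outcome stops.

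The stopping reason is not a neutral one such as administrative closure. Eligibility rests on organ function, white cell count, performance status, prior therapy and disease type, any of which may relate to prognosis. Censoring for that reason need not be independent of survival, and the Kaplan-Meier method assumes that it is. For a removed patient in remission, relapse would no longer be observed. A response first seen after removal would not be recorded.

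**Working it through.** The plan gives no figure on this point to reproduce. The check is a comparison of texts, followed by an illustration of size.

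**1. The texts side by side, for a dosed patient found ineligible**

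| Source | What ends follow-up |
|---|---|
| Protocol 7.1.2 | Completion of safety follow-up (last dose + 28 days) |
| Protocol 7.1 | Not ended by stopping treatment; schedule assessments and survival follow-up continue |
| Protocol 7.1.1 | Survival followed to the end of the study, whatever the reason for stopping |
| Protocol Section 8 | Survival: consent withdrawn or study ends. Disease: progression or consent withdrawn. Responders: relapse followed until death |
| SAP 7.2.1.1 | Survival: death, loss to follow-up, study closure or consent withdrawn |

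Only 7.1.2 makes ineligibility an end to follow-up.

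**2. Size for overall survival (assumed inputs)**

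The documents give neither the number of ineligible dosed patients nor their prognosis. Assumptions:
- A fraction f of 3%, 5% or 10% is removed. With the 66 patients planned for Part A, that is about 2 to 7 patients (66 × 0.03 = 2.0; 66 × 0.10 = 6.6).
- Removed patients are censored at c = 1 or 2 months.
- True 6-month survival is 40% in eligible patients and s (10% to 60%) in ineligible patients.
- Hazards are constant, and no death is recovered after removal.

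The all-dosed value is 0.40(1 − f) + s·f.

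The large-sample Kaplan-Meier value is [(1 − f)·0.40^(c/6) + f·s^(c/6)] × 0.40^((6−c)/6), because only eligible patients remain at risk after c.

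Worst case upward (f = 0.10, s = 0.10, c = 1):
- (0.90 × 0.8584 + 0.10 × 0.6813) × 0.4660 = 0.392
- All-dosed value: 0.36 + 0.01 = 0.370
- Shift: +2.2 points

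Worst case downward (f = 0.10, s = 0.60, c = 1):
- (0.90 × 0.8584 + 0.10 × 0.9184) × 0.4660 = 0.403
- All-dosed value: 0.36 + 0.06 = 0.420
- Shift: −1.7 points

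Kaplan-Meier value against all-dosed value, with the shift in points, at c = 1:

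| f | s = 10% | s = 20% | s = 40% | s = 60% |
|---|---|---|---|---|
| 3% | 39.8 v 39.1 (+0.7) | 39.9 v 39.4 (+0.5) | 0 | 40.1 v 40.6 (−0.5) |
| 5% | 39.6 v 38.5 (+1.1) | 39.8 v 39.0 (+0.8) | 0 | 40.1 v 41.0 (−0.9) |
| 10% | 39.2 v 37.0 (+2.2) | 39.6 v 38.0 (+1.6) | 0 | 40.3 v 42.0 (−1.7) |

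At c = 2 and f = 10% the extremes shrink to +1.5 (38.5 v 37.0) and −1.4 (40.6 v 42.0).

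For scale, the standard error of a 40% proportion in 66 patients, ignoring censoring, is √(0.40 × 0.60 / 66) = 0.060, or 6 points. The largest shift is well inside that.

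**3. Does removal come before response can be assessed?**

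Protocol 11.6.1.3 schedules marrow at Cycle 1 Day 30 ± 1 and at end of treatment. Even a patient dosed only on Day 1 stays until Day 1 + 28 = Day 29, the opening of that window. One last dosed on Day 4 stays until Day 32. The first response assessment therefore largely survives. What 7.1.2 loses is later response and relapse assessment.

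**The case against.** **The specific rule governs.** Section 7.1 points to 7.1.2, so 7.1.2 could be read as a deliberate exception. Nothing in 7.1.1, Section 8 or SAP 7.2.1.1 recognises one, and the survival estimand has no such exclusion. If an exception is intended, its effect on the all-dosed analysis is not stated. The inconsistency stands.

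**The SAP recovers survival.** SAP 7.2.1.1 asks sites to establish the status of withdrawn patients at the final survival analysis from notes, hospital records, general practitioners and death registries. Protocol 7.3 adds a vital-status search, though under loss to follow-up. This has force: a reader might infer that survival is always censored 28 days after the last dose, and the documents do not support that. Some deaths may be recovered. Response and relapse data would not be.

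**Effect on the Part B decisions.** A reader might infer that removals in Cohort B2 would materially raise the chance of a futility result. The documents do not support attributing that to 7.1.2. The first marrow usually falls before removal, and the Part B rate is calculated after the opportunity for one cycle (protocol 11.7.2.2). Lost responses would come mainly from stopping treatment, which 7.1 requires separately. That 7.1.2 applies to a B2 patient not confirmed centrally is itself an inference from its wording on patients who fail the criteria after starting.

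**Historic marrow samples.** A reader might add that inclusion criterion 13 asks for a fresh pretreatment marrow while 11.6.1.3 and 12.6.1.3 accept a historic one, so those patients would be removed too. The allowance is for otherwise eligible patients with Medical Monitor approval, and they are plainly meant to be treated. That mismatch is a separate drafting matter.

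**Practical effect.** Part B never opened, and the SAP records recruitment stopped on 16 June 2023 with a planned last visit on 8 August 2023, so follow-up was short for everyone. SAP version 2.0 dropped its own sections on time to response and duration of response, although its Section 13 would apply protocol 11.7.6 to Part A where data allow. Survival is a descriptive secondary endpoint with no hypothesis test. All of this limits the consequence.

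**Conclusion.** The contradiction is real and worth correcting, but its likely effect is small. Section 7.1.2 cuts active survival, response and relapse follow-up for patients who remain in the all-dosed set, for a reason that may relate to prognosis, while every other relevant section continues it.

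Under the stated assumptions (3% to 10% removed, no deaths recovered), 6-month survival shifts by about −1.7 to +2.2 points, and by zero if ineligible patients have the same prognosis. Deaths recovered through the SAP status check would reduce the shift. The direction cannot be predicted, because the documents say nothing about the prognosis of ineligible patients. No claim is made about the Part B go or stop probabilities.

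**What to change.** - **Protocol 7.1.2:** replace removal from the study with continued disease-response and survival follow-up under the schedule of activities, subject to consent, in line with 7.1, 7.1.1 and Section 8.
- **Protocol 11.3.1, Cohort B2:** state that a patient enrolled on a local TP53 result that is not confirmed centrally stays in the intention-to-treat set and in follow-up.
- **Study treatment:** whether it continues in these patients is for the sponsor to reconcile across the sections. No position is taken here.

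The cost is wording and a few more assessments and monthly survival contacts for patients already in the trial. No sample size or decision threshold changes.

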7.2 Patient Withdrawal from the Study

A patient may withdraw from the study at any time at his/her own request. A patient who considers withdrawing from the study must be informed by the Investigator about modified follow-up options (eg, telephone contact, a contact with a relative or treating physician, or information from medical records). Patients may be withdrawn at any time at the discretion of the Investigator for safety, behavioural, compliance, or administrative reasons; this is expected to be uncommon.

If the patient is on study treatment, this will be discontinued and the patient will be withdrawn from the study at this time. An EoT visit should be conducted at the time of withdrawal from the study, if it has not already been performed.

If the patient withdraws consent for disclosure of future information, the sponsor may retain and continue to use any data collected before such a withdrawal of consent. If a patient withdraws from the study, it should be confirmed if he/she still agrees for existing samples to be used in line with the original consent. If he/she requests withdrawal of consent for use of samples, destruction of any samples taken and not tested should be carried out in line with what was stated in the informed consent and local regulation. The Investigator must document the decision on use of existing samples in the site study records and inform the Global Study Team.

Patients that are withdrawn from the study but are evaluable per the definition of DLT-evaluable (Section 11.7.3) will not be replaced. Patients who do not experience a DLT (Section 11.4.7) can be replaced if the patient withdraws before the end of the DLT window. Any patient that is withdrawn and is not evaluable will be replaced to ensure a minimum number of evaluable patients.

7.2.1 Procedures for Withdrawal from Study

Patients who withdraw from the study will always be asked about the reason(s) and the presence of any AEs. If possible, they will be seen by an Investigator and undergo the assessments and procedures scheduled for the post-study assessment. AEs should be followed up and study treatment should be returned by the patient.

7.3 Lost to Follow-up

A patient will be considered lost to follow-up if he or she repeatedly fails to return for scheduled visits and is unable to be contacted by the study site.

The following actions must be taken if a patient fails to return to the clinic for a required study visit:

- The site must attempt to contact the patient and reschedule the missed visit as soon as possible and counsel the patient on the importance of maintaining the assigned visit schedule and ascertain whether or not the patient wishes to and/or should continue in the study.
- Before a patient is deemed lost to follow-up, the Investigator or designee must make every effort to regain contact with the patient (where possible, 3 telephone calls and, if necessary, a certified letter to the patient's last known mailing address or local equivalent methods). These contact attempts should be documented in the patient's medical record.
- Should the patient continue to be unreachable, he/she will be considered to have withdrawn from the study.
- Site personnel, or an independent third party, will attempt to collect the vital status of the patient within legal and ethical boundaries for all patients enrolled in the study, including those who did not get study treatment. Public sources may be searched for vital status information. If vital status is determined as deceased, this will be documented and the patient will not be considered lost to follow-up. Sponsor personnel will not be involved in any attempts to collect vital status information.

Discontinuation of specific sites or of the study as a whole are handled as part of [Appendix A](#).

8 STUDY ASSESSMENTS AND PROCEDURES - CORE

The study assessments listed in this section apply to all modules. Safety assessments specific to each module will be listed in the respective sections. Study procedures and their timing are summarised in the SoA of each individual module. Protocol waivers or exemptions are not allowed.

Immediate safety concerns should be discussed with the Medical Monitor immediately upon occurrence or awareness to determine if the patient should continue or discontinue study treatment. Adherence to the study requirements, including those specified in the SoA for each module, is essential and required for study conduct.

The maximum amount of blood collected from each patient during the first 28 days of treatment for research assessments is not anticipated to exceed 275 mL.

Enrolment and Screening

At enrolment, each potential patient will provide informed consent prior to starting any study-specific procedures (see [Appendix A 3](#)). Screening will take place for up to 28 days from the date of enrolment. Every effort should be made to minimise the time between treatment

assignment and dosing, preferably to within 14 days. Patients who fail to meet the eligibility criteria will be recorded as a “screen failure”. Individuals who do not meet the criteria for participation in this study (screen failure) may be re-screened up to 2 times. Each potential patient is assigned a unique patient number. If a patient withdraws from the study, then the patient number cannot be reused.

All screening evaluations must be completed and reviewed to confirm that potential patients meet all core and module-specific eligibility criteria. The Investigator will maintain a screening log to record details of all patients screened and to confirm eligibility or record reasons for screening failure, as applicable. The common screening forms will be considered as core protocol in the electronic data capture (EDC) system.

Procedures conducted as part of the patient’s routine clinical management (eg, blood count) and obtained before signing of the ICF may be utilised for screening or baseline purposes provided the procedures met the protocol-specified criteria and were performed within the appropriate time frame relative to the first dose of study treatment, as defined in the SoA.

Demographic data and other characteristics will be recorded and will include gender, race, and ethnicity according to local regulations. A standard medical history, medication history, and surgical history will be obtained during review of the selection criteria. This will include the date of initial diagnosis of the disease under study, disease assessment within 28 days prior to the first dose of AZD0466, prognostic indices/disease profiling (if available from local laboratory results) for each disease indication, and all prior anticancer treatments (including responses and duration of response) for the disease under study.

Disease assessments and other clinical data obtained as standard of care (SoC) prior to consent may be used for the study, provided the assessments fall within the protocol-specified period prior to the first dose of study treatment.

Follow-up Period

The EoT assessment will be performed at the time study treatment is permanently discontinued. In addition, patients should be followed up for 28 days after the last dose of study treatment for any new AEs, follow-up of existing AEs and other study assessments. Patients should also be asked about concomitant medications at this follow-up. Patients will continue to be followed until disease progression or withdrawal of consent. All patients should be followed monthly for survival after the last clinic visit until withdrawal of consent or end of study for the purpose of assessing survival status (see Section 7.1). Patients who achieve a complete remission (CR) or CR with incomplete haematological recovery (CR_i) should be followed for relapse of disease until death.

